2.2 Secondary Objectives (or Aim)

The secondary objectives are to:

- Assess treatment initiation and adherence and family engagement as mediators of intervention treatment effects
- Explore individual, family, and community factors that moderate intervention treatment effects.
- Investigate test-retest reliability of PFCC survey
- Investigate intervention group parent satisfaction with the care manager
- Evaluate intervention group outcome experience with care management and study feedback

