5.5 Sample Size and [name]

Aim 1: The investigative team assumed that there will be 240 evaluable children parent-child dyads (from 300 enrolled), and that these will be divided 1:1 across the two groups. From these assumptions, power analyses we conducted based on simulations, in which two groups of 120 children were generated, followed over 3 time periods (totaling 9-12 months), where the measurements were correlated from baseline to 6-8 months (corr=0.8) and from baseline to 9-12 months (r=0.6). The investigative team assumed that the true differences between treatment groups was a score of 5.0 units over time. Once a dataset was simulated, a marginal model for longitudinal data was applied (GEE with a first order auto-regressive working correlation structure and robust variance estimates). For comparing the effect of the intervention, power of 0.87 was found to detect a difference of 2.5 points along the Vanderbilt score (assuming a standard deviation of 6 points, and a difference of 2 points assuming a standard deviation of 5). These good levels of power are achievable with the longitudinal design.

Aim 2: For the outcomes of initiation and adherence, binary outcomes were assumed and performed analyses using the PASS 13 software (Hintze, 2011). For the purposes of this study, the ADHD PGI will be used to determine the level of initiation and adherence. Initiation is defined as starting a treatment plan for which one has moderate to greater preference. Adherence is defined as the continuation of treatment through month 9-12. Assuming that the tier 1 group of 120 children experiences a 50% rate of initiation and adherence, power would be about 0.89 to detect an increase in that rate among the tier 2 group to 70% and would be greater than 0.98 to detect an increase to 75%.

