
We conducted sensitivity analyses to examine the impact of preference and treatment intensity on the main outcome of ADHD symptoms. We stratified tier 2 participants by intervention dosage (frequency of interaction with the portal/care manager): 0-1 sessions, 2 sessions, or 3 or more sessions. We compared differences in ADHD symptom score changes over time by intervention dosage using a linear mixed effects model that adjusted for seasonality.

Aim #2: We originally proposed to assess whether family engagement, treatment initiation and adherence were mediators of intervention treatment effects: This analysis proposed to focus on the role of engagement and treatment initiation at 3 months or adherence at 6 and 9 months as mediators of the effect of the intervention on the study outcomes. Since none of the primary or secondary outcome measures were different between groups, we elected not to proceed with formal tests of mediation. Instead, we assessed for differences in family engagement and treatment initiation and adherence between groups. For each of the above sets of potential mediators, we report distributions by case/control as assess bivariate differences via t-tests or contingency tables/Chi-square analyses where appropriate.

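### Mediation, a stated secondary objective, was dropped after the results because no outcome differed between arms; that reason does not exclude an indirect effect, and the replacement tests only the first path

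*SAP*

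**What the plan says.** Protocol section 2.2 lists as its first secondary objective: "Assess treatment initiation and adherence and family engagement as mediators of intervention treatment effects". The measures table in section 4.5.1 marks engagement, medications and the SACA as mediators. Section 5.5 gives power under Aim 2, but only for the arm difference in initiation and adherence. The protocol specifies no mediation model and no power for an indirect effect.

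The SAP, written in the past tense, says under Aim #2 that mediation had been proposed, with engagement and initiation at 3 months and adherence at 6 and 9 months as the mediators. It then reports: "Since none of the primary or secondary outcome measures were different between groups, we elected not to proceed with formal tests of mediation". What was done in its place: "Instead, we assessed for differences in family engagement and treatment initiation and adherence between groups". Those comparisons are t-tests and chi-square tests, with mixed models for the engagement domains. The SAP describes no mediator-to-outcome model and no indirect effect. It gives no equivalence margin or confidence interval to support the statement that the outcomes did not differ.

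**The concern.** The decision makes a protocol objective conditional on a significant total effect, and it was taken once the outcomes were known. Two inferences in the SAP's sentence fail. Non-significance is not evidence that the arms are equal. And a total effect that is small, or that sums two opposing parts, can coexist with a real indirect effect.

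The replacement analysis asks whether the care manager moved engagement or treatment use. It cannot say whether a change in treatment use was accompanied by a change in symptoms, or how large any indirect effect could be. The objective in section 2.2 is therefore unanswered. The gate was also not applied evenly: moderation, another secondary objective, went ahead under SAP Aim #3 with three-way interactions and subgroup analyses.

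**Working it through.** **Inputs from protocol section 5.5.** Sample: "240 evaluable children parent-child dyads (from 300 enrolled), and that these will be divided 1:1 across the two groups", so 120 per arm. Mediator: "Assuming that the tier 1 group of 120 children experiences a 50% rate of initiation and adherence", rising to 70% or 75% in tier 2. Outcome SD: 6 points. Alpha is not stated; 0.05 two-sided is assumed. The effect of the mediator on the outcome, b, is not in the documents. It is an assumption and is varied below.

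**Reproducing the plan's Aim 2 power.** The protocol says "power would be about 0.89 to detect an increase in that rate among the tier 2 group to 70" per cent, and "would be greater than 0.98 to detect an increase to 75" per cent. For 50% versus 70%, the pooled rate is 0.60:

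- SE under the null = √(2 × 0.60 × 0.40 / 120) = 0.0632
- SE under the alternative = √((0.25 + 0.21) / 120) = 0.0619
- Power = Φ((0.20 − 1.96 × 0.0632) / 0.0619) = 0.890

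The same steps for 75% give 0.983. Both stated figures reproduce, which supports the assumed alpha.

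**Aim 1.** The protocol says "power of 0.87 was found to detect a difference of 2.5 points along the Vanderbilt score" at SD 6. A simple single-time comparison gives 0.898. The stated value came from a GEE simulation that is not fully specified, so this is not an exact match. The 2-point, SD 5 case gives 0.873. With an SE of 6 × √(2/120) = 0.775, the unadjusted total-effect test needs about 0.775 × (1.96 + 0.84) = 2.17 points for 80% power.

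**Total-effect test against joint test, no direct effect, b = 3.**

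- Total effect = 0.20 × 3 = 0.6 points. Power = Φ(0.6/0.775 − 1.96) + Φ(−0.6/0.775 − 1.96) = 0.12.
- First path: 0.89, as above.
- Second path: 60 + 84 = 144 children with the mediator and 96 without. SE = 6 × √(1/144 + 1/96) = 0.791. Power = Φ(3/0.791 − 1.96) = 0.97.
- Joint = 0.890 × 0.967 = 0.86. Simulation agrees.

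For b = 2 and b = 4, the total effect is 0.4 and 0.8 points, total-effect power is 0.08 and 0.18, and joint power is about 0.63 and 0.89.

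**Could the planned 2.5 points run wholly through this mediator?** It would need b = 2.5 / 0.20 = 12.5 points, or 2.1 SD. In tier 1 the mediator would then contribute 12.5² × 0.25 = 39 units of variance, more than the outcome's 36. At the protocol's own shift, a plausible indirect effect is well below what the total-effect test was sized to find.

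**Where the ordering changes** (simulation, 4,000 runs per row for the 50% scenarios; the 80% rows follow the formulas above and agree with simulation):

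| Scenario | Total-effect test | Joint test |
|---|---|---|
| 50% vs 70%, indirect 1.0, direct −1.0 | 0.05 | 0.89 |
| 50% vs 70%, total 2.5, indirect 1.0 | 0.90 | 0.88 |
| 50% vs 70%, total 2.5, indirect 0.5 | 0.90 | 0.78 |
| 50% vs 70%, total 2.5, indirect 0.2 | 0.90 | 0.22 |
| 50% vs 55%, b = 5, no direct effect | 0.07 | 0.11 |
| 80% vs 90%, b = 3, no direct effect | 0.07 | 0.46 |
| 80% vs 85%, b = 3, no direct effect | 0.05 | 0.14 |

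The 80% rows are an assumption prompted by the documents. Children must already be receiving ADHD treatment (section 3.4.1), and section 1.3 says 80% of treated children receive medication. For 80% versus 90%, the first path has power 0.58 and the second, with 204 against 36 children, 0.79; 0.58 × 0.79 = 0.46.

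Baseline adjustment (r = 0.6) raises total-effect power for a 1.0-point effect only from 0.25 to 0.37.

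**Timing of the mediators.** SAP Aim #2 describes medication status at baseline, 3, 6 and 9 months. Protocol sections 4 and 4.5.1 put the SACA at 9-12 months. Engagement is at 0 and 9-12 months in section 4, at 9-12 months in section 4.4.2 (the PFCC questionnaire), and at 3 months in the section 4.5.1 table and SAP Aim #2. Medication status is therefore the only mediator that the SAP clearly describes as measured before the later outcomes.

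**The case against.** The retained analyses answer much of the practical question. Arm differences in treatment use, read beside the randomised arm difference in symptoms, already help to separate a care manager who did not change uptake from uptake that changed without benefit. Formal mediation adds only the mediator-to-symptom link, which is not randomised. This largely stands as mitigation, but it leaves the objective as written unanswered.

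A reader might infer that the total-effect test is generally far weaker than a mediation test. The table does not support that: with a substantial same-direction direct effect the total-effect test does as well or better, and with a weak first path both are poor. The 50% versus 70% contrast was also set for initiation and adherence defined through the ADHD PGI, whereas the SAP uses service use and on/off medication. The 0.86 therefore does not carry over to medication status.

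The joint test's apparent power also assumes no confounding. In simulation with a true mediator effect of zero and an unmeasured factor loading 0.2, 0.3 or 0.4 on both mediator and outcome, it rejected 6%, 16% and 44% of the time. Adjustment for baseline score would reduce this by an unknown amount.

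The indirect effects at issue (0.4 to 0.8 points for b = 2 to 4) are small beside the planned 2 to 2.5 points and would not alter the primary conclusion. Uncertain temporal order for engagement would have been a sound reason for caution, but it is not the reason given. Finally, the SAP states the original plan, the change and its reason openly, so nothing in it suggests concealment.

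**Conclusion.** The concern holds in this form: a stated secondary objective was dropped after the results were seen, for a reason that does not justify dropping it, and the replacement covers only the first path. The possible loss ranges from large (0.12 against about 0.86 at 50% versus 70%, b = 3) to slight (0.05 against 0.14 at 80% versus 85%). These figures rest on an assumed b, SD 6, 120 per arm, two-sided alpha 0.05, no direct effect and no mediator-outcome confounding.

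A reader might go further and infer that an indirect effect was present and missed. The documents give no mediator results and no outcome estimates, so they support no such statement. If the arms did not differ on the mediators, a sizeable indirect effect would be less likely.

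**What to change.** Remove the significance gate from SAP Aim #2 and label the original omission a post-hoc, results-driven departure from the protocol. Then:

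- Estimate mediation whatever the total-effect p-value, labelled exploratory, for medication status at the 3-month visit with outcomes at the later visits.
- Report the arm-to-mediator path; the mediator-to-outcome path adjusted for baseline score, baseline medication status and the other Aim 1 baseline covariates; and the indirect and direct effects with bootstrap 95% confidence intervals. State the assumption of no unmeasured mediator-outcome confounding beside the estimates. The SAP does not say whether the Aim 1 medication covariate is baseline or time-varying; here it should be the baseline value.
- For the SACA and engagement, where the mediator is measured at 9-12 months with the final outcome, report associations only and say that temporal order cannot be established. Reconcile the engagement timings in protocol sections 4, 4.4.2 and 4.5.1 and in SAP Aim #2.
- Report the primary arm differences as confidence intervals against the planned 2.5 points (2 points at SD 5), in place of the statement that the outcomes did not differ.

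The cost is a few days of analysis on data already collected, plus wording. The downside is a non-randomised, exploratory estimate that may be imprecise if medication use is already high.

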4.4.2 Other Evaluations, Measures

To measure ADHD symptoms, we will use the NICHQ Vanderbilt Assessment Follow Up— PARENT Informant (Appendix 9) Scale, a follow-up form of the Vanderbilt Parent Rating Scale (VPRS) a standard validated measure of ADHD symptom severity that is commonly employed in clinical care and ADHD research studies, at baseline and 3-5 months, 6-8 months, and 9-12 months (Wolraich et al., 1998; Wolraich, et al., 2003). The VPRS is a public domain tool that consists of parent forms (separate from teachers, the Vanderbilt Teacher Rating Scale, or VTRS) and includes 18 items corresponding to the DSM-5 ADHD symptom criteria, 8 items that screen for opposition-defiant disorder, 7 items that screen for conduct disorder, and 12 items that screen for anxiety and depression. The Vanderbilt Follow Up items from the VPRS are scaled on a 4-point Likert rating ("never" to "very often"), but the scales used in this study will be restricted to the 18 ADHD symptom items and the 8 Performance Items, excluding further questions regarding Medication. In validation studies, the internal consistency of the VPRS and VTRS were excellent (alpha=0.90-0.94), and concurrent validity was high (r=0.79) in relation to diagnostic interviews. The Vanderbilt scale will permit us to compare effects between treatment arms and with the results of other studies. These scores have been identified as important by clinician stakeholders and will be provided to practices to assist with ADHD management.

To determine goal attainment, patient and family treatment goals will be identified through use of the ADHD PGI. Goal Attainment Scaling (GAS), will then be used to allow parents to rate the degree to which each of their goals, identified using the ADHD PGI, is met (Grissom, Erchul, & Sheridan, 2003; Jitendra et al., 2007; Sheridan, Eagle, Cowan, & Mickelson, 2001). The GAS response categories are ordered from -2 ("situation got significantly worse") to +2 ("goal completely met"). Parents will complete the GAS (Appendix 5) at 3-5 months, 6-8 months, and 9-12 months.

The PFCC questionnaire will be administered at month 9-12 to assess family engagement as mediators of intervention treatment effects. Up to 40 participants will receive this questionnaire 10-21 days after completing their 9-12 month study measures to examine test-retest reliability. The study team developed this questionnaire. Questionnaire items are based

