on the semi-structured interviews of caregivers. The participants interviewed identified critical dimensions of caregiver engagement in the treatment of ADHD. Participants also completed a card sort procedure to rate the importance of engagement questionnaire items for one or more outcome domain. An alternative group of parents who completed the card sort procedure also participated in cognitive interviews. Cognitive interviews were used to evaluate the appropriateness and understandability of caregiver engagement questionnaire items for parents of children with ADHD. A cognitive debriefing technique identified problematic phrasing and elicited alternative words and phrases that parents use to describe the item concepts. Prior to completing the questionnaire parents will be able to identify whom they consider part of their ADHD study team. Then parents will rate to the degree in which they are engaged in their child's ADHD treatment planning and implementation

The satisfaction survey will be administered after month 9-12 to families in the intervention arm to evaluate their satisfaction with having a care manager. This will consist of 8 questions scaled on a 5-point Likert scale ("Strongly Disagree" to "Strongly Agree"). This survey will also include two open-ended questions, "What did you like about the care manager program?" and "How would you suggest improving the care manager program?".

The qualitative interview will be conducted after the 9 month care management is complete with the intervention arm to assess their experience with care management and for study feedback. This will consist of 9 open-ended questions (Appendix 20 Qualitative Interview)

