In order to assess family engagement, a series of items were created from review of the literature and prior instruments in other fields. We utilized confirmatory factor analyses to find distinct domains for which each item loading was greater than 0.7. Our first round of analyses resulted in 3 factors: patient/family centered care, communication, and understanding. Upon presentation to the study team, there were several items that were dropped from the initial domains, but additional items resonated with the team as important concepts in which the intervention was focused. Thus, the study team came to consensus on items that should be included. These items represented four conceptual domains. The 4factor structure was supported in confirmatory factor analyses. While the patient/family centered care and understanding domains remained the same, the original communication domain was split into two factors, resulting in the following domains: care team accessibility; patient and family-centered care; communication among members of the care team, and understanding of ADHD. To compare patients in the tier 1 and tier 2 groups by engagement status, we utilized t-tests for each of the four domains separately. Further, linear mixed effects models were implemented for each engagement domain as the outcome, with intervention status and season as covariates clustering for clinic site. We further assessed for item responsiveness using item response methods.

We explored treatment initiation and adherence via the services assessment for children and adolescents (SACA) and medication status.⁹⁵ On the SACA, patients reported service use ever, as well as service use within the past 9 months. Categorizations include any service use, ambulatory service use (any community mental health or outpatient clinic, private professional, or in-home provider), and overnight stay (psychiatric or medical unit, residential treatment center, group home, or foster home). Differences between intervention groups and treatment initiation were assessed via Chi-square tests. In addition, treatment initiation and adherence were assessed via medication status throughout the study period. At baseline and 3, 6, and 9 month follow up surveys, participants were asked as to whether their child was on or off medication. If data was missing for a particular timepoint, we utilized medication status within the EHR if available.

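### Two of the four family-engagement domains were settled after a first factor solution, with items added to match the intervention, so a Tier 2 advantage on them need not mean broader engagement

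*SAP*

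**What the plan says.** Protocol section 4.4.2 says of the PFCC questionnaire: "The study team developed this questionnaire". Its items came from caregiver interviews, a card sort and cognitive interviews. On timing and purpose, "The PFCC questionnaire will be administered at month 9-12 to assess family engagement as mediators of intervention treatment effects". For reliability, "Up to 40 participants will receive this questionnaire 10-21 days after completing their 9-12 month study measures". Before answering, parents define the group they are rating: "Prior to completing the questionnaire parents will be able to identify whom they consider part of their ADHD study team". Sections 5.2 and 5.3.2 plan only internal consistency and test-retest reliability for this measure. They give no scoring key and no plan to reselect items.

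The SAP, under Aim #2, describes how the scores were reached:

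- **Starting rule:** "We utilized confirmatory factor analyses to find distinct domains for which each item loading was greater than 0.7". This gave three factors: patient/family-centred care, communication and understanding.
- **Revision:** after the solution was presented to the team, some items were out, but "additional items resonated with the team as important concepts in which the intervention was focused". Then "the study team came to consensus on items that should be included".
- **Result:** communication became two factors, one on how accessible the care team is and one on communication within it. The SAP says the other two domains did not change, and that confirmatory factor analysis supported four factors.
- **Use:** Tier 1 and Tier 2 are compared on each of the four domains by t-test, and by a mixed model with arm and season as covariates and clustering by clinic site.

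The SAP does not name the factor-analysis sample, does not say whether the team had seen data by arm, and does not label the four domains post hoc.

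**The concern.** Two separate matters are involved.

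The first is what the scores mean. Items entered because they matched the intervention's focus, and the domain that changed is the one closest to the care manager's job. Protocol sections 1.2 and 4.2 give the care manager the tasks of passing information between parties and coordinating care. A Tier 2 parent may also count the care manager as part of the team being rated, and parents are not blinded. A higher Tier 2 score on accessibility or team communication may therefore record that a care manager was present. It need not show that the family was more engaged in planning and carrying out ADHD treatment, which is what section 4.4.2 says parents rate.

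The second is the word confirmatory. A structure revised after seeing a first solution and then refitted to the same responses has not been tested independently.

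Because the SAP drops formal mediation tests, these between-arm comparisons are what remains of the engagement question in Aim #2. Their interpretation therefore matters. The primary ADHD symptom analysis is not affected.

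**Working it through.** The documents give no sample size, power or item-level figure for the PFCC comparison, so there is no plan figure to reproduce. The check has three parts.

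**1. Which data and which domains?**
Table 1 and section 4.4.2 of the protocol place the PFCC at 9-12 months, plus a retest in up to 40 participants. The earlier development work was qualitative. The likeliest factor-analysis sample is therefore the trial's own 9-12 month responses, but this is an inference. Protocol section 4 also places an engagement measure at 0 and 9-12 months, and the table in section 4.5.1 has a separate engagement row at month 3. Taking the SAP at its word that two domains were unchanged, the revision bears on two of the four scores.

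**2. Does choosing items this way create a false arm difference?**
Simulation with 120 per arm (the evaluable number in protocol section 5.5). Everything else is assumed: 12 candidate items, 5 kept, one common factor, loadings 0.5 and 0.75, two-sided 0.05, 4000 runs, no true arm difference. Rejection rates:

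| Items chosen by | Loading 0.5 | Loading 0.75 |
|---|---|---|
| Content | 0.050 | 0.052 |
| Pooled loadings | 0.051 | 0.042 |
| Observed arm difference | 0.206 | 0.103 |

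Only the third row is inflated, and nearly all of its rejections favour Tier 2 (0.205 and 0.100). No passage says items were chosen that way.

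**3. How far can intervention-matched items enlarge an apparent engagement effect?**
Assume a domain of 5 items with inter-item correlation 0.6. Each added item carries a true 0.4 SD arm difference and the other items carry none.

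- Variance of the domain mean = (1 + 4 × 0.6)/5 = 0.68, so SD = 0.825.
- Shift per added item = 0.4/5 = 0.08, which is 0.08/0.825 = 0.097 SD.
- Two items: 0.16/0.825 = 0.19 SD. Three items: 0.24/0.825 = 0.29 SD.
- Range: at correlation 0.4 the variance is 0.52, the SD 0.721 and the shift per item 0.111 SD. At correlation 0.8 they are 0.84, 0.917 and 0.087 SD. The shift scales in proportion to the assumed 0.4.

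The same simulation with a true 0.3 SD shift on 5 of the 12 items (loading 0.75) gives 0.36 SD and 81% rejection on the five matched items, against 0.16 SD and 24% on all twelve. A closed-form check agrees:

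- Inter-item correlation is 0.75² = 0.5625.
- Five items: variance (1 + 4 × 0.5625)/5 = 0.65, and 0.3/√0.65 = 0.37.
- Twelve items: shift 0.3 × 5/12 = 0.125, variance (1 + 11 × 0.5625)/12 = 0.599, and 0.125/√0.599 = 0.16.

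Item choice does not produce an effect from nothing. It can more than double the apparent size of a narrow one (0.36/0.16 = 2.25).

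**The case against.** The strongest reply is that engagement was a hypothesised mediator, and a mediator measure ought to cover what the intervention targets. The trial is about communication and shared decisions, so a parent who counts the care manager as part of the team may simply be reporting the intervention at work. Communication was also already a first-round factor, so going back to three domains would not remove it. This stands, and it is why the split domains should be kept and reported. It does not make them a measure of engagement in general.

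Other objections also stand in part:

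- Item content came from interviews, literature and prior instruments before the 9-12 month responses. Only item retention and domain structure could have depended on those data.
- The SAP does not say that the added items loaded below 0.7, or whether the loading rule or the team removed the dropped ones. A breach of the rule is therefore not shown.
- The illustrative sizes rest on assumed inputs, and the item shifts in them are real differences on narrow items.

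A reader might go further and infer that all four comparisons are compromised, that the scale was constructed from end-of-study data, or that the comparison is biased toward Tier 2. The documents do not support any of these. Two domains are stated to be unchanged, the items predate the responses, and selection that ignores arm keeps the error rate near 0.05. Directional bias would need items to be picked on observed arm differences, which the documents neither state nor rule out.

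**Conclusion.** The point holds as a matter of interpretation and labelling for two of the four engagement domains. Items matched to the intervention were brought in after a first factor solution, and communication was split into two domains close to the care manager's role. The resulting structure is described as confirmed with no independent sample named. A Tier 2 advantage confined to those two domains would not show that families were more engaged in a broader sense.

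The possible enlargement cannot be computed from the documents. Under the stated assumptions it is about 0.10 SD per added item in a five-item domain (0.087 to 0.111 across correlations of 0.8 to 0.4).

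The conclusion assumes that the factor analyses used the trial's own responses, which is likely but not stated. If an independent sample was used, the objection to the word confirmatory falls away and the point about meaning remains. Neither document reports an engagement result. This should be changed, but it does not bear on the primary analysis.

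**What to change.** - Report the arm comparison on the first-round three-domain scores, or on a total over all administered PFCC items, alongside the four domains.
- Label the two split domains and the four-factor structure post hoc and exploratory. Alternatively, fit the structure in one random half of respondents and test it in the other.
- State which sample and time point the factor analyses used, and whether item selection was blind to arm. Reconcile the engagement timings in protocol sections 4, 4.4.2 and 4.5.1 and Table 1.
- List the items dropped and added, with their loadings and final domain.
- Do not conclude that engagement in general differed if the difference appears only in the two split domains.

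The cost is some wording and a few extra scores from data already held. The small downside is that the domains the team prefers become exploratory.

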3.4.1 Inclusion Criteria

- 1) Aged 5 through 12 years old
- 2) Receiving ADHD treatment from participating practices
- 3) ADHD or ADD diagnosis code, ICD-10-CM F90.9 or F90.0, listed in the problem list or recorded at an ambulatory visit in the past year.
- 4) Parental/guardian permission (informed consent) and if appropriate, child assent.

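### SAP Aim 2 reads treatment initiation from prevalent use in children already in ADHD treatment, which is not the protocol's definition and dilutes any difference between arms

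*SAP*

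**What the plan says.** **Entry.** Protocol 3.4.1 requires "Receiving ADHD treatment from participating practices".

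**Definition.** Protocol 5.5 (Aim 2) defines initiation as the start of a treatment plan that the family prefers at least moderately. It defines adherence as continuing treatment through month 9-12. The ADHD PGI is named as the instrument for both.

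**Power.** The same section plans on a single rate covering both outcomes: "Assuming that the tier 1 group of 120 children experiences a 50% rate of initiation and adherence". On that basis "power would be about 0.89 to detect an increase in that rate among the tier 2 group to 70" per cent, and it "would be greater than 0.98 to detect an increase to 75" per cent.

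**Analysis.** SAP Aim 2 explores initiation and adherence together through two sources. On the SACA, "patients reported service use ever, as well as service use within the past 9 months". For medication, at baseline and at 3, 6 and 9 months, "participants were asked as to whether their child was on or off medication", with EHR status filling gaps. Initiation is compared between arms by chi-square. The SAP does not say which SACA window is the initiation variable. It gives no rule separating a new start from continued use, and it does not mention the PGI or preference.

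**Timing of the SACA.** Protocol 4 and the table in 4.5.1 place it once, at 9-12 months. Protocol Table 1 marks a general row for treatment initiation and adherence at baseline and at every later visit, without naming the instrument.

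**The concern.** Starting a treatment is an event, and only a child not yet on that treatment can have it. Use at some time, or being on medication at a visit, is a state that a child can carry in from before randomisation. Because entry requires current ADHD treatment, some children will be in that state at baseline. They then count as positive in both arms whatever the care manager does, and the two rates move together.

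The SAP reports that the primary and secondary outcomes did not differ and that formal mediation tests were therefore dropped. These between-arm comparisons are what remains of Aim 2 on whether the care manager changed treatment use. A null result on a diluted measure could be read as no effect on initiation, when initiation as the protocol defines it was not measured. The protocol's planning rates and power would also be attached to a different outcome.

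**Working it through.** **Inputs.** Protocol 5.5 gives 240 evaluable dyads of 300, split 1:1, so n = 120 per arm, with 50% in tier 1 against 70% or 75% in tier 2. Alpha is not stated for Aim 2; two-sided 0.05 is assumed. The share f of each arm already using the treatment at baseline is not in the documents and is varied.

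**Formula.** Two-proportion z test with pooled variance under the null:

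power = Φ{[Δ − 1.96·√(2p̄(1−p̄)/n)] / √([p1(1−p1)+p2(1−p2)]/n)}

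**Step 1: the protocol's own figures.**
- 50% vs 70%: p̄ = 0.60. The null SE is √(2×0.60×0.40/120) = 0.0632 and the alternative SE is √((0.25+0.21)/120) = 0.0619. (0.20 − 0.1240)/0.0619 = 1.23, so power is 0.890.
- 50% vs 75%: p̄ = 0.625, with SEs 0.0625 and 0.0604. (0.25 − 0.1225)/0.0604 = 2.11, so power is 0.983.

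Both stated powers reproduce. They treat all 120 children per arm as able to have the outcome.

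**Step 2: prior users counted as initiators.** Assume that 50% vs 70% holds among baseline non-users. The observed rates become f + (1−f)×0.50 and f + (1−f)×0.70, so the difference shrinks to (1−f)×0.20. At f = 0.50 the rates are 75% and 85%. (0.10 − 1.96×0.0516)/0.0512 = −0.02, so power is 0.49.

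**Step 3: restricted to baseline non-users.** The contrast returns to 50% vs 70%, but n falls to (1−f)×120. At f = 0.50, n = 60. (0.20 − 1.96×0.0894)/0.0876 = 0.28, so power is 0.61.

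| f (assumed) | Observed rates | Power as analysed (120 per arm) | Non-users per arm | Power, non-users only | Recovered by restricting |
|---|---|---|---|---|---|
| 0 | 50% vs 70% | 0.89 | 120 | 0.89 | 0 |
| 0.25 | 62.5% vs 77.5% | 0.72 | 90 | 0.79 | 0.07 |
| 0.50 | 75% vs 85% | 0.49 | 60 | 0.61 | 0.12 |
| 0.80 | 90% vs 94% | 0.21 | 24 | 0.29 | 0.08 |

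**Step 4: splitting the loss.** At f = 0.50 the fall from 0.89 to 0.49 is 0.40. The choice of analysis accounts for 0.12 (0.61 − 0.49). The other 0.28 (0.89 − 0.61) comes from having 60 rather than 120 children at risk per arm. At f = 0.80 the split is 0.08 and 0.60.

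**Where f might lie.** Protocol 1.3 cites literature in which 80% of treated children receive medication and fewer than half receive behavioural interventions. Those figures are not from this sample. They make a high f plausible for medication and a lower one plausible for services, so one value need not suit both measures.

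**The case against.** The other side has several fair points.

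- **A reader might infer that initiation is tested on lifetime service use.** The SAP does not say so. It records both windows and names neither as the initiation variable. Past-9-month use at a month-9 visit largely excludes use that ended before randomisation. What stands is that continuing users still count, and the window is unspecified.
- **A reader might infer that the recall window misses the first months after randomisation.** With a 9-month window that is true only of late visits: at month 12 it would omit months 0-3. Protocol 1.3 describes the SACA recall as the previous 9-12 months, which could cover the whole of follow-up. The two descriptions need reconciling, but a systematic gap is not shown.
- **A reader might take the entry criterion to mean that nearly every child is already positive.** Treatment at a primary care practice does not imply a positive SACA, whose ambulatory category covers community mental health or outpatient clinics, private professionals and in-home providers. Nor does it imply medication.
- **The between-arm comparison is not biased.** Randomisation should balance prior use, so prevalent use is a legitimate, less sensitive contrast. Children already treated also belong in the adherence half of Aim 2. This stands as a defence of a comparison of use, but not of calling it initiation.
- **The analysis is exploratory.** The SAP uses that language, and no primary result depends on it. This stands and limits the severity.

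**Conclusion.** The point holds as a mismatch between definition and measure. Protocol 5.5 defines initiation as a new start of a preferred treatment, assessed with the PGI. SAP Aim 2 measures prevalent use in children already under treatment, with no at-risk restriction or baseline adjustment. Followed as written, continuing users count as initiators and dilute the arm difference by the factor (1−f).

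How much this matters here cannot be fixed from the documents, because f is unknown. The power range rests on three assumptions: f of 25%, 50% or 80%; 50% vs 70% among non-users; and two-sided alpha of 0.05. It would be wrong to present the fall from 0.89 to as little as 0.21 as the cost of the analysis choice. Restricting to non-users recovers only 0.07 to 0.12. The remaining shortfall follows from how few children can initiate, and no re-coding restores it. The 0.89 applies only if all 120 children per arm are at risk.

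This should be corrected. It does not threaten the primary outcome.

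**What to change.** **Medication.** Use the baseline status already collected. Define initiation as a first move onto medication after randomisation among children off it at baseline, and adherence as continuation among those on it at baseline. Both groups are fixed before randomisation, so each comparison remains randomised. Also compare follow-up status in all children with baseline status as a covariate.

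**SACA.** Report lifetime use descriptively, not as an initiation outcome. Name the window used and make it cover the time since enrolment. Confirm whether any baseline service measure exists, since Table 1 conflicts with Protocol 4 and 4.5.1. If there is none, label the comparison service use during follow-up and state the limitation.

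**Definition and power.** Reconcile the SAP with Protocol 5.5: either apply the PGI and preference criterion or state that it was dropped and why. Report the number at risk per arm, and say that 0.89 assumed all 120.

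**Cost.** The medication part needs only SAP wording and re-coding. The SACA part may need data that were not collected, in which case only the label can change. The denominator for initiation becomes smaller and the stated power less favourable. Because the SAP is written with results known, definitions added now should be labelled post hoc.
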